### 11.5.1 Missing Date of Investigational Product

No imputation will be applicable to missing date of investigational product.

### 11.5.2 Missing Date Information for Prior or Concomitant Medications

For prior or concomitant medications, incomplete (i.e., partially missing) start date and/or stop date will be imputed.

[figure not shown]
#### 11.5.2.1 Incomplete Start Date

The following derivations will be applied to impute the missing start dates. In each section, dates will be defined using the hierarchy of the derivations. Should any of the following start dates created be after a complete stop date provided, use the stop date as the start date, instead of the date that would otherwise be created.

##### 11.5.2.1.1 Missing Day and Month

1. If only year is known, and it is previous to the year of the informed consent, use June 30th of that year.
2. If only year is known, and it is the year of the first dose date, use the first dose date

Document: T:\PROJ\Shire\UYA25606\_Biostatistics\Documentation\SAP\SAP\SHP633-306\_SAP\_Final  
v2.0\_20180415.docx

Author: 

Version Number:  
Version Date:

Final V2.0  
15Apr2019

3. If only year is known, and it is after the year of the first dose date, then use Jan 1st of that year.
4. If only year is known, and it is the year of the informed consent, use the informed consent date.

#### **11.5.2.1.2 Missing Month Only**

The day will be treated as missing and both month and day will be replaced according to the above procedures.

#### **11.5.2.1.3 Missing Day Only**

1. If year and month are known, and it is the month and year of the first dose date, use the first dose date.
2. If year and month are known, and it is the month and year of the informed consent, use the informed consent date.
3. If year and month are known, and the month is not the month and year of the first dose or informed consent, use the first day of the month.

For other incomplete dates, leave as missing.

#### **11.5.2.2 Incomplete Stop Date**

The following derivations will be applied to impute the missing stop dates. In each section, dates will be defined using the hierarchy of the derivations. Should any of the following stop dates created be before a start date (either a complete date or an imputed one,), use the (imputed) start date instead of the date that would otherwise be created.

#### **11.5.2.2.1 Missing Day and Month**

1. If only year is known and study medication stopped during that year, use the stop date of study medication.
2. If only year is known and study medication stopped after that year, use December 31st of that year.
3. If only year is known and study medication stopped prior to that year, use the first day of the year.

Document: T:\PROJ\Shire\UYA25606\_Biostatistics\Documentation\SAP\SAP\SHP633-306\_SAP\_Final  
v2.0\_20180415.docx

Author: [REDACTED]

Version Number:

Final V2.0

Version Date:

15Apr2019

### **11.5.2.2.2 Missing Month Only**

The day will be treated as missing and both month and day will be replaced according to the above procedures.

### **11.5.2.2.3 Missing Day Only**

1. If year and month are known and study medication stopped during that month and year, use the stop date of study medication.
2. If year and month are known and informed consent was provided during that month and year, use the date of informed consent.
3. If only year and month are known and study medication stopped after that year and month, use the last day of the month.
4. If only year and month are known and study medication stopped prior to that year and month, use the first day of the month.

For other incomplete dates, leave as missing.

### **11.5.3 Missing Date Information for Adverse Events**

If any AE records contain only partial dates, these will be handled by imputation, as described in the subsections below.

#### **11.5.3.1 Incomplete Start Date**

The following derivations will be applied to impute the missing dates. In each section, dates will be defined using the hierarchy of the derivations. Should any of the following start dates created be after a complete stop date provided, use the stop date as the start date, instead of the date that would otherwise be created.

##### **11.5.3.1.1 Missing Day and Month**

1. If only year is known, and it is previous to the year of the informed consent, use June 30th of that year.
2. If only year is known, and it is the year of the first dose date, use the first dose date
3. If only year is known, and it is after the year of the first dose date, then use Jan 1st of that year.

Document: T:\PROJ\Shire\UYA25606\_Biostatistics\Documentation\SAP\SAP\SHP633-306\_SAP\_Final  
v2.0\_20180415.docx

Author: [REDACTED]

Version Number:  
Version Date:

Final V2.0  
15Apr2019

4. If only year is known, and it is the year of the informed consent, use the informed consent date.

#### **11.5.3.1.2 Missing Month Only**

The day will be treated as missing and both month and day will be replaced according to the above procedures.

#### **11.5.3.1.3 Missing Day Only**

1. If year and month are known, and it is the month and year of the first dose date, use the first dose date.
2. If year and month are known, and it is the month and year of the informed consent, use the informed consent date.
3. If year and month are known, and the month is not the month and year of the first dose or informed consent, use the first day of the month.

Otherwise, if a start date is unknown, leave as missing.

#### **11.5.3.2 Incomplete Stop Date**

No imputation is applied to incomplete stop date.

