9.8 Safety Analyses

The safety endpoints include AEs, 12-lead ECG, vital signs, laboratory safety data, antibodies to teduglutide, and 48-hour urine output, body weight, BMI and gastrointestinal-specific tests.

Adverse events will be coded using the Medical Dictionary for Regulatory Activities (MedDRA). Treatment-emergent AEs are defined as AEs that started or worsened on or after the date and time of the first dose of study dose. Treatment-emergent AEs will be summarized by system organ class and preferred term using descriptive statistics (eg, number and percentage of subjects). Adverse events will be summarized by severity, relationship to treatment, and for AEs leading to discontinuation, and death. In addition, SAEs will also be tabulated by overall and treatment-related events.

For laboratory tests, 48-hour urine output, vital signs, body weight, body mass index, and ECG variables, descriptive statistics (eg, n, mean, standard deviation, median, minimum and maximum values, the number and percentage of subjects in specified categories) will be used to summarize the absolute values and change from baseline at each time point.

The number and percentage of subjects classified as having antibodies to teduglutide will be used to summarize the presence of antibodies.

The safety population will be the analysis population for all the safety data analysis.

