## 11.5 Handling of Missing, Unused, and Spurious Data

No imputation for missing data (e.g., last observation carried forward) will be applied except for the partial dates to derive treatment emergent adverse events and flagging prior/concomitant medications.

Imputation will be performed for partial dates of AEs and medications solely for the purpose of defining treatment emergence for AEs, determining whether an AE started in the treatment period and prior/concomitant status for medications. Details on how to handle partial dates for adverse events and prior/concomitant medications are described below.

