#### **11.5.4 Missing Severity Assessment for Adverse Events**

If severity is missing for an AE starting prior to the date of the first dose of investigational product, then a severity of “Mild” will be assigned. If the severity is missing for an AE starting on or after the date of the first dose of investigational product, then a severity of “Severe” will be assigned. The imputed values for severity assessment will be used for incidence summaries only and will not be reported in the data listings.

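### The SAP's check on imputed AE start dates works only with a complete stop date, so an AE whose recorded stop month precedes dosing can be counted as treatment-emergent (minor)

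*SAP*

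**What the plan says.** The current text is SAP v2.0; v1.0 has the same rules.

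- **Start with only the year known** (SAP 11.5.3.1.1, rule 2): "If only year is known, and it is the year of the first dose date, use the first dose date".
- **Start with only the month missing** (SAP 11.5.3.1.2): "The day will be treated as missing and both month and day will be replaced according to the above procedures". It therefore follows the same rule.
- **Order** (SAP 11.5.3.1): "In each section, dates will be defined using the hierarchy of the derivations". Rule 2 stands ahead of the consent-year rule (rule 4), so it wins when consent and first dose fall in the same year.
- **Check against the stop date** (SAP 11.5.3.1): "Should any of the following start dates created be after a complete stop date provided, use the stop date as the start date".
- **Partial AE stop dates** (SAP 11.5.3.2): "No imputation is applied to incomplete stop date".
- **Use of the imputed start** (SAP 11.5): "solely for the purpose of defining treatment emergence for AEs, determining whether an AE started in the treatment period". SAP 7.1 sends AE records with partial dates to these rules.
- **Definition** (Protocol 9.8): "Treatment-emergent AEs are defined as AEs that started or worsened on or after the date and time of the first dose". SAP 7.1 likewise requires onset or worsening after study medication, and SAP 13 declares no change from the protocol analysis.

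**The concern.** The check in 11.5.3.1 exists to stop an imputed start from falling after the event was over. Because it is limited to complete stop dates, it does not act on a stop date recorded as month and year, even when that month is wholly before the first dose. Two AEs with the same history are then classed differently according to whether the day of the stop was written down, which has no bearing on whether the event preceded drug.

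Pre-dose AEs will be on file. Protocol 8.1 collects them from consent, and Protocol 3.2 allows up to 17 weeks of screening, optimization and stabilization. A misclassified AE would enter the treatment-emergent incidence tables and the severity and relationship breakdowns in SAP 7.1. With at least 5 treated subjects planned, one subject is a visible fraction of any row.

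**Working it through.** The plan states no figure to reproduce. The check applies the written rules to test records.

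**Assumed dates.** Consent 5 Mar 2018, first dose 18 Jun 2018. The lead time is 26 + 30 + 31 + 18 = 105 days, inside the protocol maximum of 17 × 7 = 119 days. The AE start is recorded as 2018 only.

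**Rules applied in order.** Rule 1 (year before the consent year) does not apply. Rule 2 does, so the start becomes 18 Jun 2018. The stop-date check then acts only on a complete stop date.

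| Recorded stop | Start under SAP rules | Treatment-emergent under SAP | Latest possible stop | Treatment-emergent with the fix |
|---|---|---|---|---|
| 20 Apr 2018 | 20 Apr 2018 | No | 20 Apr 2018 | No |
| APR2018 | 18 Jun 2018 | Yes | 30 Apr 2018 | No |
| JUN2018 | 18 Jun 2018 | Yes | 30 Jun 2018 | Yes |
| 2018 | 18 Jun 2018 | Yes | 31 Dec 2018 | Yes |

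Only the second row is wrong. That AE ended by 30 Apr 2018 at the latest, 31 + 18 = 49 days before the first dose, yet its derived onset is the first-dose date. It cannot have worsened on drug either: Protocol 8.1.1 has worsening after the first dose recorded as a new AE.

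**Conditions for the error.** All three must hold:
1. the start has no known month and its year is the first-dose year;
2. the stop date is partial;
3. the stop month is known and precedes the first-dose month.

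A start with a known month goes to 11.5.3.1.3, where a pre-dose month other than the first-dose month gives a pre-dose start.

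**Whether the calendar allows it.** The subject needs pre-dose study time in an earlier month of the first-dose year. With first-dose dates spread evenly over a 365-day year (an assumption):
- lead time of 4 weeks: 308/365 = 84%;
- lead times of 5, 9, 13 and 17 weeks: 334/365 = 92%, that is, every date outside January.

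These shares show that the situation can arise. They say nothing about how often dates are recorded this way.

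**Effect on a table row.** One added subject moves the incidence by 100/N points: 20 at N = 5, and 10 at an assumed N = 10. If the subject already has a treatment-emergent AE in that row, the subject count does not move and only the event count rises by one.

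**The case against.** The strongest reply is that such a record should seldom survive to analysis. AEs are recorded at every pre-dose visit (Protocol Table 1), and optimization visits are about 2 weeks apart (Protocol 7.1.2). Data entry is expected within about 3 business days with monitoring against source (Protocol 9.1), and omissions are queried (Protocol 9.2). An AE with an unknown start month and a known stop month inside the study period is an obvious query. This stands, and it is why the point is minor.

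Second, Protocol 9.3 leaves missing-data handling to the SAP, and counting doubtful onsets as treatment-emergent is a sound conservative choice. That stands where the timing is unknown, as in the last two table rows. It does not cover a record whose stop month rules out onset after dosing.

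Third, 11.5.3.2 only declines to impute; it does not forbid comparing a recorded month with the first dose. This also stands. The operative defect is the restriction to a complete stop date in 11.5.3.1. But no rule calls for the comparison, and 7.1 and 11.5 let the imputed start decide.

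Fourth, the result would be visible. Partial dates appear with dashes in the output (SAP 11.1), all efficacy analyses are descriptive, and the error adds treatment-emergent AEs and cannot hide one. All of that is correct and limits the harm.

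A reader might go further and infer inflated counts of severe or related events. SAP 11.5.4 does begin "If the severity is missing for an AE starting on or after the date of the first dose of investigational product" and assigns the worst grade, and 11.5.5 treats a missing relationship similarly. But this needs a further blank field on the same record, and Protocol 8.1.1 and 8.1.2 require both assessments.

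**Conclusion.** The rule is wrong as written, but minor. Followed exactly, SAP 11.5.3.1 and 11.5.3.2 class an AE as treatment-emergent when the recorded data show that it ended before the first dose, and this contradicts Protocol 9.8 and SAP 7.1. The error is confined to the three conditions set out in the working. The documents do not say how often they will be met; given prospective collection and queries, probably rarely. The 20-point figure is a ceiling that needs exactly 5 subjects and no other treatment-emergent AE for that subject in the row.

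A reader might infer that the SAP counts pre-dose AEs as treatment-emergent in general, or that it puts a rival definition in place of the protocol's. The documents support neither. A complete stop date before dosing is handled correctly, a start with a known earlier month is handled correctly, and 7.1 agrees with the protocol in substance. This is a gap in one imputation rule.

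**What to change.** In SAP 11.5.3.1, extend the stop-date check to the latest date consistent with the recorded stop date: the complete date if there is one, otherwise the last day of the known month, or 31 December if only the year is known. If that latest date is before the first dose, the imputed start is set no later than it and the AE is not treatment-emergent. Section 11.5.3.2 can stay as it is, because the latest date serves only as a bound and no stop date is stored or reported.

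The medication rules in 11.5.2.2 should not be copied for this purpose: they move an imputed stop that falls before the start forward to the start, which would leave the AE error in place.

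Optionally, for consistency, read a partial stop date the same way in the unknown-onset rule of SAP 7.1.

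The cost is one sentence and a small change to the derivation code, with no new data. AEs whose stop could fall on or after the first dose remain treatment-emergent, so the conservative default is kept.

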#### **11.5.4 Missing Severity Assessment for Adverse Events**

If severity is missing for an AE starting prior to the date of the first dose of investigational product, then a severity of “Mild” will be assigned. If the severity is missing for an AE starting on or after the date of the first dose of investigational product, then a severity of “Severe” will be assigned. The imputed values for severity assessment will be used for incidence summaries only and will not be reported in the data listings.

#### **11.5.5 Missing Relationship to Investigational Product for Adverse Events**

If the relationship to investigational product is missing for an AE starting on or after the date of the first dose of investigational product, a causality of “Related” will be assigned. The imputed values for relationship to the investigational product will be used for incidence summaries only and will not be reported in the data listings.

### 11.5.6 Character Values of Clinical Laboratory Variables

Quantitative laboratory measurements reported as “< X”, i.e. below the lower limit of quantification (BLQ), or “> X”, i.e. above the upper limit of quantification (ULQ), will be converted to X for the purpose of quantitative summaries, but will be presented as recorded, i.e. as “< X” or “> X” in the listings.

### 12. ANALYSIS SOFTWARE

Statistical analyses will be performed using Version 9.4 (or newer) of SAS® (SAS Institute, Cary, NC, US) on a suitably qualified environment.

### 13. CHANGES TO ANALYSIS SPECIFIED IN PROTOCOL

There is no change of analysis from protocol.

## 15. APPENDICES

### Appendix I – MedDRA Terms Corresponding to Each Grouping of Adverse Event of Special Interest

Groupings	System Organ Class (SOC)	Preferred Terms (PT)	Higher Level Group Terms (HLGTs)
Tumor promoting ability	Neoplasms benign, malignant and unspecified		
Growth preexisting polyps		Duodenal polyp	
		Intestinal polyp	
		Rectal Polyp	
		Large intestine polyp	
		Gastrointestinal polyp	
Benign neoplasia GI			Gastrointestinal neoplasms benign
			Hepatic and biliary neoplasms benign
		Abdominal wall cyst	
		Abdominal wall neoplasm benign	
		Benign abdominal neoplasm	
		Benign gastrointestinal neoplasm	
		Benign mesenteric neoplasm	
		Benign pancreatic neoplasm	
		Benign peritoneal neoplasm	
		Benign small intestinal neoplasm	
		Gastric haemangioma	
		Gastrointestinal polyp	
		Gastrointestinal polyp haemorrhage	

Document: T:\PROJ\Shire\UYA25606\_Biostatistics\Documentation\SAP\SAP\SHP633-306\_SAP\_Final  
v2.0\_20180415.docx

Author:

Version Number:

Final V2.0

Version Date:

15Apr2019

Groupings	System Organ Class (SOC)	Preferred Terms (PT)	Higher Level Group Terms (HLGTs)
		Gastrointestinal tract adenoma	
		Gingival cyst	
		Intestinal angioma	
		Intestinal cyst	
		Intestinal polyp	
		Intra-abdominal haemangioma	
		Intraductal papillary mucinous neoplasm	
		Large intestine benign neoplasm	
		Mesenteric cyst	
		Pancreatic cyst	
		Pancreatic cyst rupture	
		Peutz-Jeghers syndrome	
		Retroperitoneum cyst	
		Small intestine polyp	
		Stoma site polyp	
		Adenolymphoma	
		Ameloblastoma	
		Benign salivary gland neoplasm	
		Buccal polyp	
		Cementoblastoma	
		Dental cyst	
		Gingival polyp	
		Lip neoplasm benign	
		Mouth cyst	
		Odontogenic cyst	
		Oral fibroma	
		Oral haemangioma	
		Oral neoplasm benign	
		Oral papilloma	
		Papillary cystadenoma lymphomatosum	

Document: T:\PROJ\Shire\UYA25606\_Biostatistics\Documentation\SAP\SAP\SHP633-306\_SAP\_Final  
v2.0\_20180415.docx

Author: [REDACTED] Version Number: Final V2.0  
Version Date: 15Apr2019

Groupings	System Organ Class (SOC)	Preferred Terms (PT)	Higher Level Group Terms (HLGTs)
		Pleomorphic adenoma	
		Salivary gland adenoma	
		Salivary gland cyst	
		Tongue cyst	
		Tongue neoplasm benign	
		Tongue polyp	
		White sponge naevus	
		Anal polyp	

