7.2.3.6 Gastrointestinal-specific Testing

Gastrointestinal testing will be done for all subjects during the screening period. Follow-up testing will be performed as necessary according to the guidelines noted below.

Colonoscopy/Sigmoidoscopy

A colonoscopy/sigmoidoscopy of the remnant colon with polyp removal will be performed prior to teduglutide exposure (during stabilization if not completed within 6 months prior to screening) in subjects with any colon remnant including a rectal stump. This will be repeated at Visit 10 (or early termination). The date and result of colonoscopy are to be recorded in the eCRF.

Abdominal Ultrasound

An abdominal ultrasound will be performed prior to teduglutide exposure (during stabilization) if this procedure was not performed during the 6 months prior to screening (however, the results of the procedure must be documented).

Upper GI Contrast Series with Small Bowel Follow-through

Upper GI contrast series with small bowel follow-through will be required for all subjects with a history of Crohn's disease and will be performed during the stabilization period, prior to the baseline visit.

Esophagogastroduodenoscopy

Esophagogastroduodenoscopy (EGD) will be performed on all subjects prior to teduglutide exposure (during the stabilization period if not completed within 6 months prior to screening). Esophagogastroduodenoscopy will be repeated at Week 24/Visit 10 (or ET) for subjects with any of the following risk factors:

- Age 40 or over at Week 24/Visit 10/ET
- History of H pylori gastritis
- History of atrophic gastritis
- History of intestinal metaplasia or dysplasia in the stomach

For subjects that do not have any of the above risk factors, EGD may be repeated at Visit 10/ET at the discretion of the investigator. The dates and results of all EGDs are to be recorded in the eCRF.

48-Hour Oral Fluid Intake and Urine Output

Subjects will be provided with urine collection containers (as needed) in order to collect 48-hour urine during the 2 days prior to study visits as required. The center staff will contact the subject at least 48 hours before the scheduled visits to remind the subject to start measuring I/O, and to record these measurements into the diary. During the 48-hour measurements, the subject should maintain their usual oral fluid intake. 48-hour urine output measurements will also be collected prior to all interim safety visits.

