8.1.1 Severity Categorization

The severity of AEs must be recorded during the course of the event including the start and stop dates for each change in severity. An event that changes in severity should be captured as a new event. Worsening of pretreatment events, after initiation of investigational product, must be recorded as new AEs (for example, if a subject experiences mild intermittent dyspepsia prior to dosing of investigational product, but the dyspepsia becomes severe and more frequent after first dose of investigational product has been administered, a new AE of severe dyspepsia [with the appropriate date of onset] is recorded on the appropriate eCRF).

The medical assessment of severity is determined by using the following definitions:

Mild: A type of AE that is usually transient and may require only minimal treatment or therapeutic intervention. The event does not generally interfere with usual activities of daily living.

Moderate: A type of AE that is usually alleviated with specific therapeutic intervention. The event interferes with usual activities of daily living, causing discomfort but poses no significant or permanent risk of harm to the research subject.

Severe: A type of AE that interrupts usual activities of daily living, or significantly affects clinical status, or may require intensive therapeutic intervention.

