### 7.1 Adverse Events

AEs will be coded using MedDRA. Investigator verbatim as well as PT and SOC will be included in the listings.

Treatment emergent AEs (TEAEs) are defined as AEs whose onset occurs, severity worsens, or intensity increases after receiving the study medication. AEs with an unknown date of onset and a stop date after the start of the study treatment or unknown stop date will be included as TEAEs. Any AE with a start date equal to the date of first dose, where the time of the AE cannot definitively place the start of the AE prior to the first dose, will be considered treatment emergent. If any AE records contain only partial dates, these will be handled by imputation, as described in [Section 11.5.3](#). AEs which are not treatment emergent will be flagged in listings.

AEs will be summarized overall using descriptive statistics (e.g., number and percent of subjects). The number of events will also be presented. Categories summarized will include any TEAEs, severity of TEAEs, investigator assessment of relationship of TEAEs to study treatment, treatment emergent serious AEs (TESAEs), severity of TESAEs, investigator assessment of relationship of TESAEs to study treatment, TEAEs leading to death, and TEAEs leading to study treatment discontinuation.

TEAEs will be summarized using number and percentage of subjects. Subject incidence for AEs within each SOC and PT will be presented, unless otherwise specified. The number of events will also be presented. Categories summarized are as follows:

- TEAEs,
- Severity of TEAEs,
- Investigator assessment of relationship of TEAEs to study treatment,
- TESAEs.

Presentation by SOC and PT will present SOC sorted alphabetically and PT within SOC by descending incidence.

Listings will be provided for serious adverse events (SAEs), AEs leading to death, AEs leading to study treatment discontinuation and AEs leading to study discontinuation. Adverse events leading to study discontinuation are not captured in the AE eCRF page, however primary reason for study discontinuation due to AE is capture in the End of Study eCRF page with the relevant AE number. This data will be used to present the AE leading to study discontinuation. The listings will be sorted by subject identifier and will include SOC, PT, reported term, start date/time, end date/time, frequency, severity, relationship, action taken, and outcome.

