### 7.1.1 Adverse Events of Special Interest

An AE of special interest is an AE (serious or nonserious) of scientific and medical concern specific to the sponsor's product or program and for which ongoing monitoring and immediate notification by the investigator to the sponsor is required.

The AEs of special interest that require expedited regulatory reporting for this study include the following:

- Growth of preexisting polyps of the colon
- Benign neoplasia of the GI tract including the hepatobiliary system
- Tumor-promoting ability (e.g., benign and/or malignant neoplasia of any kind, not limited to those of the GI or hepatobiliary system)

The preferred terms corresponding to each grouping of events of special interest will be identified by Takeda. A listing indicating the MedDRA terms corresponding to each grouping of events of special interest can be found in [Appendix I](#).

For each grouping of events of special interest, PT, the number and percentage of subjects with at least one TEAE of special interest will be presented. The number of events of special interest will also be summarized.

Listing for AE of special interest will also be provided.

Document: T:\PROJ\Shire\UYA25606\_Biostatistics\Documentation\SAP\SAP\SHP633-306\_SAP\_Final  
v2.0\_20180415.docx

Author: 

Version Number:

Final V2.0

Version Date:

15Apr2019

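### SAP Appendix I fills the polyp-growth group of special-interest events with five polyp terms that carry no growth and only partly name the colon, so a new or duodenal polyp would be tabulated as growth

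*SAP*

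**What the plan says.** Protocol section 8.3 and SAP v2.0 section 7.1.1 give the category in the same words: "Growth of preexisting polyps of the colon". The original protocol, which is the one SAP section 1 cites, has the same wording as Amendment 1, so this is not a version difference.

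SAP 7.1.1 says the sponsor identifies the preferred terms for each group and points to Appendix I for them. For each group and preferred term, "the number and percentage of subjects with at least one TEAE of special interest will be presented". It adds no condition on growth, on presence at baseline or on site.

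Appendix I labels the group "Growth preexisting polyps" and lists five preferred terms. The other two groups are *Tumor promoting ability*, filled by a whole system organ class, and *Benign neoplasia GI*, filled by two higher-level group terms and a long list of preferred terms.

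SAP 7.1 states: "Treatment emergent AEs (TEAEs) are defined as AEs whose onset occurs, severity worsens, or intensity increases after receiving the study medication". Protocol 8.1.1 states: "Worsening of pretreatment events, after initiation of investigational product, must be recorded as new AEs". On display, SAP 7.1 states: "Investigator verbatim as well as PT and SOC will be included in the listings". SAP 7.1.1 also provides an AESI listing.

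**The concern.** The category has three parts: the lesion grew, it was there before, and it was in the colon. The mechanism that assigns events to it tests none of the three fully. It looks only at the preferred term, and a polyp term says that a polyp was reported, not that it enlarged or pre-dated treatment.

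The recording rules do not help. A new polyp is treatment-emergent because its onset is after dosing. A worsened one is also entered as a new event. Both arrive in the table under the same preferred term.

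At stake is what a reader takes from a row headed as polyp growth in a small single-arm study of a drug for which neoplasia is the stated safety interest. A count there would be read as evidence that existing colon lesions enlarged on treatment, when the inputs cannot show that.

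**Working it through.** The plan gives no figure to reproduce. The check is a term-by-term comparison of the Appendix I group with the category in protocol 8.3.

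| Term in the growth group | Expresses growth or pre-existence | Site | Also under Benign neoplasia GI |
|---|---|---|---|
| Large intestine polyp | No | Large bowel | Yes |
| Rectal polyp | No | Rectum | Yes |
| Intestinal polyp | No | Not colon-specific | Yes |
| Gastrointestinal polyp | No | Not colon-specific | Yes |
| Duodenal polyp | No | Outside the colon | Yes |

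Counts:
- Growth or pre-existence in the term: 0 of 5.
- Site: 2 large bowel or rectum + 2 not colon-specific + 1 outside the colon = 5.
- Overlap with Benign neoplasia GI: 5 of 5, so every subject in the growth row is also in that row.

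The rectum is treated as in scope because protocol 7.2.3.6 examines the remnant colon "in subjects with any colon remnant including a rectal stump".

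Four cases run through SAP 7.1 and 7.1.1 as written:

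1. *A new colon polyp, coded Large intestine polyp.* It is treatment-emergent by onset and its term is in the group. The row counts it as growth. The protocol category does not apply.
2. *A duodenal polyp, coded Duodenal polyp.* The row counts it as growth. The protocol category does not apply, whether or not the polyp grew. The case can arise: protocol 7.2.3.6 repeats esophagogastroduodenoscopy at Week 24 or early termination in subjects with listed risk factors, including age 40 or over.
3. *A colon polyp that grew, coded Large intestine polyp.* The row counts it correctly.
4. *A colon lesion that grew, coded Colon adenoma or Rectal adenoma.* Neither term is in the growth group, so the row misses it. Both terms are listed under Benign neoplasia GI.

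So the row can include events that are not growth (cases 1 and 2) and omit one that is (case 4).

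Scale: protocol section 4 plans at least 5 dosed subjects. With 5 in the Safety Population, one subject in case 1 or 2 gives 1/5 = 20.0% in the growth row. The documents give no polyp rate, so the expected number of mislabelled events cannot be estimated.

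**The case against.** The strongest reply is that the displays already deal with this. Preferred terms are shown within each group, so a duodenal polyp prints under its own name. Verbatim terms are in the listings. With about five subjects, each event can be read individually. Expedited reporting under protocol 8.3 rests on the investigator's notification, not on Appendix I. Most of this stands, and it is why the point is minor. It does not repair the table. The by-term display exposes only the duodenal case. It cannot show whether a polyp was new or had grown, or where an unspecified intestinal or gastrointestinal polyp lay. The endoscopy summary in SAP 5.2 has three categories (normal, and abnormal with or without clinical significance) and does not show it either.

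A second reply is that the list is a deliberately broad search. It is not consistently broad: Duodenal polyp is in, while Small intestine polyp, which Appendix I lists under Benign neoplasia GI, is out. A broad search would also need a label that does not assert growth.

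A third is that SAP section 1 places table and listing specifications in a separate document, so final titles and footnotes are unseen. That is fair, and they may already be better worded. The term list is fixed in the SAP itself, however, and it decides what is counted.

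Two stronger readings are tempting, and the documents do not support them:

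- A reader might infer that adenoma-coded lesions appear only under Benign neoplasia GI. The *Tumor promoting ability* row takes in a whole system organ class, and the documents do not give its membership. Such lesions may fall there too. What can be said is that they are absent from the growth row.
- A reader might infer that a Week 24 polyp is probably new, because "A colonoscopy/sigmoidoscopy of the remnant colon with polyp removal will be performed prior to teduglutide exposure". The protocol is not uniform on when an earlier examination can stand. Table 1 footnote g requires that it was normal. The synopsis, 7.2.1.2 and 7.2.3.6 require only that it was done within 6 months before screening. With that difference and no polyp rate, no statement about new versus grown is justified.

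**Conclusion.** The mismatch holds. As the SAP is written, a new polyp or a duodenal polyp coded to one of the five terms is tabulated as growth of a preexisting polyp, and a grown lesion coded as an adenoma is not. The size is minor: one mislabelled descriptive safety row in an untested single-arm study.

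Nor should it be read as lost safety data. Each of the five terms is tabulated again in another group, the individual events are listed, and no decision rule depends on the row.

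The conclusion assumes that groups are filled by the Appendix I terms with no further filter, as 7.1.1 reads, and that the separate output specifications do not add a growth or site condition.

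**What to change.** 1. Remove Duodenal polyp from the growth group. It stays under Benign neoplasia GI.
2. Retitle the tabulated row so that it does not assert growth, for example *Colorectal and unspecified-site intestinal polyps (new or preexisting)*. Keep the protocol's category name in the AESI listing, and flag there the events whose reported verbatim term states growth of a preexisting colon polyp. The protocol category is then still reported, from what the investigator wrote.
3. Footnote that adenoma-coded lesions are not in this row, and that the three AESI groups overlap and must not be summed.

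The cost is an edit to Appendix I and section 7.1.1, one table title, one listing flag and two footnotes. No new data are needed, because the verbatim term is already planned for the listings. The downside is small: a few events of unspecified site stay in a broader row.
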